2.5.3 Handling of remaining intercurrent events of primary estimand

No remaining inter-current events are expected.

2.5.4 Handling of missing values not related to intercurrent event

Other missing data are expected to be intermittent missing data and will be assumed to be missing at random. Imputation details for data missing at random in the washout model has been provided in Section 5.7.1.

2.5.5 Sensitivity analyses for primary endpoint/estimand

The following sensitivity analyses will be performed for the primary estimand, to assess the robustness of the estimation in the presence of deviations from the assumptions specified in the primary analysis on the FAS only:

Novartis	For business use only	Page 25
SAP amendment 4		CKJX839C12301

- Linear mixed-effect model for repeated measures (MMRM) analysis without multiple imputation
- MMRM analysis on the imputed datasets, and multiple imputation will be based on a control-based pattern mixture model
- ANCOVA using the washout model including the following fixed effects: baseline concomitant lipid-modifying therapies, baseline age group, region, and a treatment-by-region interaction.

Due to the limited sample size of some countries, pooled regions will be used as the fixed effect for ANCOVA model. Analyses using the MMRM will include fixed effects for treatment, baseline age group (\geq 12-<15 or \geq 15-<18 years of age), visits, interaction between treatment and visits, baseline LDL-C. Day 90, 150, 270, 330 and 360 will be included as visit. The Restricted Maximum Likelihood (REML) estimation approach will be used with covariance structure set as "Unstructured". If the model does not converge with unstructured covariance matrix, the compound symmetry covariance matrix will be used in the mixed model.

The control-based pattern mixture model, as specified in Section 5.7.2, will be used to further explore the possibility of missing data being missing not at random. This approach will utilize placebo data for monotone missing inclisiran treatment data. Same MMRM as specified above will be used on analyze the imputed datasets.

2.5.6 Supplementary analysis

Supplementary analyses of LDL-C percent change from baseline to Day 330 will be performed in subgroups as specified in Section 2.2.1. The MMRM model (using control-based pattern mixture model for missing value imputation) will be used to evaluate the difference between inclisiran and placebo groups in each subgroup. Forest plot will be provided for sub-group analyses.

2.6 Analysis of the key secondary objective

2.6.1 Key secondary endpoints

The following are key secondary efficacy endpoints:

- Time-adjusted percent change in LDL-C from baseline after Day 90 and up to Day 330 (Year 1), defined as the average of percent changes from baseline to day 150, 270, and 330.
- Absolute change in LDL-C from baseline to Day 330 (Year 1)
- Percent change in Apo B from baseline to Day 330 (Year 1)
- Percent change in Lp(a) from baseline to Day 330 (Year 1)
- Percent change in non-HDL-C from baseline to Day 330 (Year 1)
- Percent change in total cholesterol from baseline to Day 330 (Year 1)

Secondary estimands corresponding to key secondary efficacy endpoints are defined similarly to the primary estimand. These endpoints, and the corresponding summary measures, are listed

Novartis	For business use only	Page 26
SAP amendment 4		CKJX839C12301

below. Population, treatment of interest, endpoints, and intercurrent events are defined similarly as for the primary estimand.

- Endpoint: time-adjusted percent change in LDL-C from baseline after Day 90 and up to Day 330 (Year 1). Summary measure: difference between treatment groups in mean time-adjusted percent change in LDL-C from baseline after Day 90 and up to Day 330 (Year 1).
- Endpoint: absolute change in LDL-C from baseline to Day 330 (Year 1). Summary measure: difference between treatment groups in mean absolute change in LDL-C from baseline to Day 330 (Year 1).
- Endpoint: percent change in Apo B from baseline to Day 330 (Year 1). Summary measure: difference between treatment groups in mean percent change in Apo B from baseline to Day 330 (Year 1).
- Endpoint: percent change in Lp(a) from baseline to Day 330 (Year 1). Summary measure: difference between treatment groups in mean percent change in Lp(a) from baseline to Day 330 (Year 1).
- Endpoint: percent change in non-HDL-C from baseline to Day 330 (Year 1). Summary measure: difference between treatment groups in mean percent change in non-HDL-C from baseline to Day 330 (Year 1).
- Endpoint: percent change in total cholesterol from baseline to Day 330 (Year 1). Summary measure: difference between treatment groups in mean percent change in total cholesterol from baseline to Day 330 (Year 1).

2.6.2 Statistical hypothesis, model, and method of analysis

The key secondary endpoints will be analyzed using the same ANCOVA with multiple imputation using wash-out model as mentioned for primary endpoint except the time-adjusted percent change in LDL-C from baseline after Day 90 and up to Day 330. In the model baseline LDL-C will be replaced by baseline of respective endpoint. The estimate and corresponding 2-sided 95% confidence intervals of mean difference between treatment groups will be calculated. P-value for hypothesis test for mean difference will also be provided.

The time-adjusted percent change in LDL-C from baseline after Day 90 and up to Day 330 will be estimated using MMRM model. MMRM analysis (using control-based pattern mixture model for missing value imputation) will be performed on the percentage change in LDL-C from baseline over visits (Day 150, 270, 330) as specified for primary endpoint on each of the 100 imputed dataset. Then, linear combinations of the estimated means from visits Day 150, 270 and 330 will be used to compare treatment effects in terms of time-adjusted percent change in LDL-C. Treatment effects from these 100 MMRM analyses will then be combined using Rubin's Method. The estimate and corresponding 2-sided 95% confidence intervals of mean difference between treatment groups will be calculated. P-value for hypothesis test for mean difference will also be provided.

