⁹ Apo B, Lp(a), non-HDL-C, total cholesterol, triglycerides, HDL-C, VLDL-C and Apo A1 in addition to the separately listed LDL-C (see Section 8.3 for details).

Novartis	
Amended Protocol Version 02 (Clean)	

Page 46 of 90 Protocol No. CKJX839C12301

Period	Screening ¹		Part 1 (D	ouble-bl	ind, place	bo-contro	lled)		Part 2 (Open-labe	el, single-a	arm)	Follow-up
Visit Name	Screening	Day 1 (Baseline & 1st Treatment)		Day 90	Day 150	Day 270	Day 330	Day 360 ("Switch Day") ²	Day 450	Day 510	Day 630	Day 720 (End of Treatment/ Study) ³	Safety follow-up (last visit +30 days) ⁴
Days	-28	1	30	90	150	270	330	360	450	510	630	720	750
¹⁰ ADA serum sampl ¹¹ Diagnosis of diabe	etes based on fa	asting plasma	glucose	(FPG) sh	ould be ve							d.	

Confidential

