8.3.2 Other efficacy biomarkers

Other efficacy assessments will include:

• Apo B, Lp(a), non-HDL-C, total cholesterol, triglycerides, HDL-C, VLDL-C, Apo A1, PCSK9

Samples for these additional efficacy biomarkers will be collected on Days 1, 90 (PCSK9 only), 150, 330, 360, 510 and 720. (Table 8-1).

After randomization (Day 1) until the Day 360 visit, the results from the efficacy laboratory assessments must be blinded to participants, investigator staff, persons performing the assessments, and the CTT.

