2.6.4 Sensitivity analyses

MMRM analysis using control-based pattern mixture model for missing value imputation will be performed for key secondary endpoints (except the time-adjusted percent change in LDL-C from baseline after Day 90 and up to Day 330) as specified for primary endpoint in Section 2.5.5. In model corresponding baseline value will be used instead of baseline LDL-C.

For the time-adjusted percent change in LDL-C from baseline after Day 90 and up to Day 330, mixed model for repeated measurements (MMRM) analysis without multiple imputation, that assumes missing data are MAR, will be performed. The model will be same as MMRM model mentioned in Section 2.6.2. A linear combination of the estimated means from visits Day 150, 270 and 330 will be used to compare treatment groups.

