5.7 Statistical models

5.7.1 Multiple Imputation Wash-out model

A multiple imputation washout model will be utilized for the primary efficacy analysis of the percentage change in LDL-C from baseline to Day 330 endpoint. The washout model can be thought of as a modified control-based PMM that will be used to explore the possibility of missing data being MNAR for subjects who discontinued the study early. For subjects who discontinued the study early, their missing values will be imputed under the assumption that their outcome would be similar to those in the placebo group with similar background characteristics. For subjects in the inclisiran group only missing Day 330 values will be imputed. For subjects in the placebo group their missing values over all visits after early termination will be used to account for uncertainty in the imputation process and results from the imputed datasets will be combined using Rubin's method. Further details are provided below.

For the placebo group the following variables will be included in a multiple imputation procedure (SAS PROC MI), this assumes missing data are MAR:

- Baseline value of efficacy measurement (continuous)
- Observed value of efficacy measurement at Day 90 (continuous)
- Observed value of efficacy measurement at Day 150 (continuous)
- Observed value of efficacy measurement at Day 270 (continuous)
- Observed value of efficacy measurement at Day 330 (continuous)
- Observed value of efficacy measurement at Day 360 (continuous)

For the subjects in the inclisiran group who completed first 3 doses and have data available after Day 330 (considered to have completed the Study Part 1) the following variables_will be included in a multiple imputation procedure (SAS PROC MI), this assumes missing data are MAR:

- Baseline value of efficacy measurement (continuous)
- Observed value of efficacy measurement at Day 330 from the inclisiran group (continuous)

For the remaining subjects in the inclisiran group the following variables will be included in a multiple imputation procedure (SAS PROC MI), this assumes missing data are MNAR:

• Baseline value of efficacy measurement (continuous)

Novartis	Confidential	Page 45 of 48
Clinical Study Report Appendix 16.1.9, v1.0		Study No. CKJX839C12301

Novartis	For business use only	Page 44
SAP amendment 4		CKJX839C12301

• Observed value of efficacy measurement at Day 330 from the placebo group (continuous)

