- 1. Intermittent missing data in the placebo treatment group will be imputed using Markov Chain Monte Carlo (MCMC) methods, assuming MAR. SAS PROC MI will be utilized for this step using the MCMC impute=monotone option. A total of 100 datasets will be created. These datasets will be utilized in Step #2.
- 2. The remaining missing values in the placebo group with a monotone missing data pattern will be imputed in this step. Missing data will be imputed assuming data are MAR. Only subjects in the placebo group will be utilized in this step. SAS PROC MI will be used to impute missing values utilizing the monotone reg option. Baseline age group will be included in the regression model. This will be performed for the 100 datasets. After this step, the 100 datasets will be fully imputed for the placebo treatment group. These datasets will be utilized in Step #4.
- 3. Subjects in the inclisiran group who received first 3 doses of study medication, have the Day 330 value missing, and have evaluable data after Day 330 will be included in this step. Missing values at Day 330 will be imputed assuming data are MAR. Only subjects in the inclisiran group will be included in this step. Observed Baseline data, Day 330 data and baseline age group will be utilized to impute missing Day 330 data utilizing SAS PROC MI. This will be performed 100 times to create 100 datasets that are fully imputed at Day 330.
- 4. The remaining missing values at Day 330 in the inclisiran group will be imputed in this step. Note that the subjects with imputed inclisiran Day 330 data from Step #3 will not be utilized in this step. Control-based PMM imputation will be performed. With this imputation model, the missing efficacy measurements in the inclisiran group will not be constructed from the observed data in the inclisiran group but rather from the observed and imputed data in the placebo group at Day 330. Baseline data and age group will also be utilized in the imputation. The MNAR statement in SAS PROC MI will be used to impute missing values. This will be performed for the 100 datasets.
- 5. The imputed data from Step #3 will be combined with the imputed data from Step #4 to create 100 fully imputed datasets.

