5.7.2 Control based Pattern-Mixture model

A control-based PMM will be used to explore the possibility of missing data being MNAR for subjects who discontinued the study. For subjects who discontinued the study without any further follow-up data, their missing values after study discontinuation will be imputed under the assumption that their outcome would be the similar to those in the placebo group with similar background characteristics. For subjects who did not discontinue the study, their intermittent missing values will be imputed based on the MAR assumption. Multiple imputation will be used to account for uncertainty in the imputation process and results from the imputed datasets will be combined using Rubin's method. Further details are provided below.

The covariates and baseline characteristics which can be predictive of the response will be included in a multiple imputation procedure (SAS PROC MI) and will include the following:

- Baseline value of efficacy measurement (continuous)
- Observed value of efficacy measurement at Day 90 (continuous)
- Observed value of efficacy measurement at Day 150 (continuous)
- Observed value of efficacy measurement at Day 270 (continuous)
- Observed value of efficacy measurement at Day 330 (continuous)
- Observed value of efficacy measurement at Day 360 (continuous)
- 1. Intermittent missing data will be imputed using MCMC methods, assuming MAR, within each treatment group. SAS PROC MI will be utilized for this step using the MCMC impute=monotone option. A total of 100 datasets will be created. These datasets will be utilized in Step #2.
- 2. The remaining missing values with a monotone missing data pattern will be imputed in this step. Control-based PMM imputation will be performed. With this imputation model, the missing efficacy measurements in the inclisiran group will not be constructed from the observed data in the inclisiran group but rather from the observed data in the placebo group. We will also use this model to impute missing efficacy measurements in the placebo group. The MNAR statement in SAS PROC MI will be used to impute missing values under the aforementioned assumptions. Baseline age group will be included in the imputation model. This will be performed for the 100 datasets. After this step, the 100 datasets will be fully imputed.

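### The SAP sends Apo B and Lp(a) to imputation models that need Day 90 and Day 270 values, which the protocol never schedules for them; a smaller point is that washout Step 3 ignores participants' own other values

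*SAP*

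**What the plan says.** **Analysis.** SAP 2.6.2 covers absolute change in LDL-C and percent change in Apo B, Lp(a), non-HDL-C and total cholesterol: "The key secondary endpoints will be analyzed using the same ANCOVA with multiple imputation using wash-out model as mentioned for primary endpoint". The one stated adaptation is that each endpoint's own baseline replaces baseline LDL-C. SAP 2.6.4 adds an MMRM after control-based PMM imputation, as set out for the primary endpoint in 2.5.5, and again changes only the baseline: "In model corresponding baseline value will be used instead of baseline LDL-C". SAP 2.6.5 reuses PMM plus MMRM for subgroups, and an MMRM without imputation for log Lp(a).

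**Visit lists.** The placebo list in 5.7.1 and the list for both arms in 5.7.2 are baseline and Days 90, 150, 270, 330 and 360. The MMRM in 2.5.5 uses the same five post-baseline visits. In 5.7.1, Step 1 reads "Intermittent missing data in the placebo treatment group will be imputed using Markov Chain Monte Carlo (MCMC) methods, assuming MAR". In 5.7.2, Step 1 reads "Intermittent missing data will be imputed using MCMC methods, assuming MAR, within each treatment group".

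**Sampling.** Protocol 8.3.2 states: "Samples for these additional efficacy biomarkers will be collected on Days 1, 90 (PCSK9 only), 150, 330, 360, 510 and 720". Protocol Table 8-1 agrees. Its full lipid profile row is not marked on Day 90 or Day 270, and footnote 9 defines that row as "Apo B, Lp(a), non-HDL-C, total cholesterol, triglycerides, HDL-C, VLDL-C and Apo A1 in addition to the separately listed LDL-C". LDL-C itself is sampled on both days.

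**Step 3 of 5.7.1.** This step takes inclisiran participants who had three doses, lack a Day 330 value and have data after Day 330. It imputes Day 330 from baseline and age group only.

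**The concern.** Apo B and Lp(a) are in the hierarchical testing sequence at one-sided 0.025. Their imputation follows a list written for LDL-C, and two of its five post-baseline visits have no scheduled sample for these lipids. A placebo participant followed to Day 360 has later values but none at Days 90 and 270, so Step 1 treats those two visits as intermittent gaps and must fill them. No completer has data to fill them from. The analysis can run only after a change that the SAP does not state. At stake is pre-specification of two confirmatory endpoints.

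Part (b) is separate and minor. Step 3 selects participants because later data exist and then does not use those data, whereas the placebo steps use every visit. Step 3 also feeds the primary LDL-C analysis.

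**Working it through.** **Inputs.** Visit lists: SAP 2.5.5, 5.7.1, 5.7.2. Sampling days: protocol 8.3.2 and Table 8-1. Early-exit mapping: SAP Table 2-1. Enrolled: 141 (SAP 1.1), which at 2:1 is about 94 inclisiran and 47 placebo. The plan gives no figure of its own to reproduce here. The effect size and SDs are blacked out and are not needed.

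**(a) Identification.** In a multivariate normal model a variance needs that visit observed in someone, and a covariance needs both visits observed in the same participant.

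- Washout placebo model, and the PMM within each arm: 6 variables, so 6×7/2 = 21 variance-covariance parameters.
- Scheduled data are baseline and Days 150, 330 and 360: 4×5/2 = 10 identified, 11 not.
- Table 2-1 can map an early-exit value to Day 90 (last visit Day 1) or Day 270 (last visit Day 150). The first adds the Day 90 variance and its covariance with baseline (2). The second adds the Day 270 variance and its covariances with baseline and Day 150 (3). The maximum is 10 + 5 = 15.
- Six pairs are never observed together, however many participants exit: 90–150, 90–270, 90–330, 90–360, 270–330 and 270–360. An exiting participant has no later visit.

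| Model for Apo B and Lp(a) | Total | Scheduled data | With mapped exits | Limited to Days 150, 330, 360 |
|---|---|---|---|---|
| Washout placebo; PMM per arm | 21 | 10 | at most 15 | 10 of 10 |
| MMRM, unstructured | 15 | 6 | at most 9 | 6 of 6 |

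The numerical rank of the information matrix gives the same counts. Including the six means, 14 of 27 parameters of the placebo model are identified on scheduled data.

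An illustrative simulation (not SAS) used 47 placebo participants, mean 100, SD 15, all correlations 0.6, three leaving before Day 330, and a non-informative prior. With Days 90 and 270 in the list, the sampler broke down in 4 of 4 runs, between iterations 234 and 318. At the iterations inspected, the Day 90 mean was 93.2 to 126.6 and its SD 22 to 75. Limited to sampled visits, 4 of 4 runs completed 3,000 iterations. The Day 330 mean was similar either way (94.7 to 101.4 against 95.0 to 102.4).

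**MMRM without imputation.** The five-visit model has 2×5 + 2 = 12 fixed-effect columns (treatment-by-visit cells, age group, baseline). With records only at Days 150, 330 and 360 the rank is 2×3 + 2 = 8. The Day 330 contrast is estimable in both the five-visit and three-visit forms.

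**(b) Step 3.** If a fraction p of an arm is imputed from predictors with squared correlation R², the variance of the arm mean is multiplied by f = 1 + (1 − R²)·p/(1 − p). Assumptions: p from 1 to 10%; R² from 0.1 to 0.4 with baseline and from 0.6 to 0.8 with the participant's own history; placebo fully observed.

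SE ratio for the difference = √[(f_base/94 + 1/47)/(f_full/94 + 1/47)].

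- Top of range (p = 10%, R² 0.1 against 0.8): f_base = 1.100, f_full = 1.022; √(3.100/3.022) = 1.013, or +1.3%.
- Bottom of range (p = 1%, R² 0.4 against 0.6): f_base = 1.0061, f_full = 1.0040; √(3.0061/3.0040) = 1.0003, or +0.03%.
- Inclisiran SD 1.5 times placebo, top of range: √[(2.25×1.100 + 2)/(2.25×1.022 + 2)] = √(4.475/4.300) = 1.020, or +2.0%.

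**The case against.** The strongest reply is that any programmer would drop the empty days, which gives the very list proposed here, and that little would change. Much of this stands. The Day 330 ANCOVA uses Day 330 values. The inclisiran steps of the washout model use only baseline, age group and Day 330. The relations among the sampled visits are themselves identified. What remains is that dropping the days is an unwritten change to the imputation of alpha-controlled endpoints. The lists in 5.7 refer to a generic efficacy measurement. Where the SAP wants different visits, as for time-adjusted LDL-C, it names them. The text under SAP Section 4 is not visible in the public copy, so nothing is drawn from it.

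A reader might infer more than the documents support:

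- *That the MMRM cannot deliver Day 330.* For log Lp(a), fitted to collected records without imputation, it can. Only the five-visit specification is wrong.
- *That stray mapped values would force the compound-symmetry fallback.* The documents do not show that any such values exist or that the fit would fail to converge.
- *That losing mapped early-exit values costs measurable precision.* The Day 90–330 and 270–330 covariances are never identified, so the data cannot show how such a value predicts Day 330.
- *That two of five post-baseline visits, or 40%, are missing data.* They were never scheduled.
- *That non-HDL-C and total cholesterol are equally affected.* Their schedule is the same, but LDL-C is normally a calculated value (SAP 2.1.1). Its component lipids may be reported at LDL-C visits; the documents do not say.

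On (b), Step 3 is fully specified and reproducible, the group entering it is narrow, and the added predictors may themselves have gaps. It is an improvement, not an error.

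**Conclusion.** (a) holds for Apo B and Lp(a). The placebo imputation (5.7.1 Steps 1 and 2, with Step 4 drawing on their output) and the PMM imputation in both arms (5.7.2 Step 1) are not identified as written. This is a stated rule that does not fit the sampling schedule, not merely missing detail. The LDL-C endpoints are unaffected. The effect on the Day 330 comparison depends on how many Day 330 values are missing, which the documents do not give. It is probably small, and a reader should not infer that any Apo B or Lp(a) conclusion would change.

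(b) holds as a small improvement at no data cost. The 0.03 to 1.3% (up to 2.0%) rests on the assumed p, R² and SD ratio; none of these comes from the documents.

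**What to change.** **(a)** For Apo B and Lp(a), specify baseline and Days 150, 330 and 360 for the imputation, and Days 150, 330 and 360 for the MMRM. Apply the same to non-HDL-C and total cholesterol if they are not reported at Days 90 and 270; if they are, say so and keep the full list for them. State how an early-exit value mapped to Day 90 or 270 is handled for these lipids and report how many there are. If such a value is used to impute Day 330, state the assumption linking the two. The places concerned are SAP 2.6.2, 2.6.4, 2.6.5, 5.7.1 and 5.7.2.

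**(b)** In 5.7.1 Step 3, add the participant's own observed LDL-C at Days 90, 150, 270 and pre-dose Day 360 (Days 150 and 360 for the other lipids). Impute any gaps in these predictors in the same missing-at-random step.

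**Timing and cost.** The SAP front matter refers to work done after the Part 1 lock, so this cannot now be pre-specified. The study report should state the visit list actually used, and any re-run should be labelled a sensitivity analysis beside the original result. No new data are needed. The cost is a reporting note, an endpoint-specific variable list in the programs and, if re-run, one labelled analysis per endpoint.
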